14.5 Urgent Safety Measures (USMs)

An urgent safety measure is an immediate change in a trial procedure or temporary halt to a trial procedure, put in place prior to approval in order to protect participants from any immediate hazard to health and safety following new safety information (SAE or other information received from an external source). The Principal Investigator may carry out USMs to protect participants from immediate harm.

15 Analysis

15.1 Main analysis

A priori, we will analyse the data normality. Considering a normal distribution of the mean differences, the main analysis will consist on a t-test on the means - difference between two dependent means (matched pairs).

The null hypothesis of this test is that the means μ_x , μ_y of pre- and post- intervention, respectively, are identical.

The null hypothesis that $\mu_x = \mu_y$ can be reformulated in terms of the difference $d_i = x_i - y_i$. The null hypothesis is then given by $\mu_d = 0$. The alternative hypothesis states that μ_d has a value different from zero:

 $H_0: \mu_d = 0$

 $\mathsf{H}_{\mathtt{l}}:\mu_{\mathtt{d}} \neq 0$

However, without the normality assumption, we will consider a non-parametric Wilcoxon test.

Further details will be found in the SAP

15.1.1 Sub-group & interim analysis

Not applicable.

16 Data storage & retention

Data collected on paper will be kept in a secured room only accessible by BRAINTRAIN researchers, for a minimum period of 5 years after publication.

Data required to support analysis of the study will be entered and stored in an MS SQL Server database hosted on servers in a secure machine room at Cardiff University. This room is locked and entry is via a swipe card system.

The database will be backed up daily and access to the database will be via secure logon (username and password) and restricted to named study personnel only, as detailed in the study's PRA log.

17 Study closure

The trial will end up to 82 weeks after its start.

18 Regulatory issues

18.1 Ethical and research governance approval

The study will be conducted in accordance with the recommendations for physicians involved in research on human participants adopted by the 18th World Medical Assembly, Helsinki 1964 and later revisions.

Ethical approval for this study was given by the Ethical Committee of the Faculty of Medicine of University of Coimbra. Research governance approval (granted by CEIC/Infarmed) will be sought after document approval.

18.2 Consent

Consent will only be considered informed following provision of adequate participant information (see attached information sheet/s and consent form). Participants will be informed that they are free to withdraw at any time and that this will not impact on current or future care.

18.3 Confidentiality

Data Confidentiality is assured as stated in the Informed Consent form, according with the Portuguese data protection regulations as per the EU directive. This document can be found attached in the appendices.

18.4 Indemnity

Although not expected due to the participation, if the subject suffers any injury as a result of any study procedures, performed according to the protocol, the subject will be reimbursed for medical expenses necessary to treat them. All procedures are reviewed by staff and all incidents reported to the persons and / or entities.

18.5 **Trial sponsorship**

Faculty of Medicine of University of Coimbra.

18.6 Funding

The **'An interventional study to improve social attention in autism spectrum disorder (ASD): a brain computer interface (BCI) approach'** study is funded by the European Commission 7th Framework Programme for Research, Technological Development and Demonstration.

18.7 Audits & inspections

The study may be participant to inspection and audit by CEIC/Infarmed.

19 Study/trial management

LBIM (Laboratory of Biostatistics and Medical Informatics of the Faculty of Medicine of University of Coimbra) will manage the study.

We will keep, weekly project team meetings, monthly study management group meetings. These meetings will be attended by researchers directly involved in running the study.

20 Data monitoring & quality assurance

LBIM (Laboratory of Biostatistics and Medical Informatics of the Faculty of Medicine of Coimbra) will manage the quality of the study.

20.1 T/SSC (Trial/Study Steering Committee)

The TSC/SSC will be established centrally for the BRAINTRAIN consortium and include external clinical and methodological experts, at least one service user and an independent statistician. Members will be required to sign up to the remit and conditions as set out in the TSC Charter.

20.2 IDMC (Independent Data Monitoring Committee)

The nature of this study makes it unlikely that a separate Data Monitoring Committee (DMC) will be required; however, this will be discussed with the TSC at their first meeting and a DMC will be set up if deemed necessary. Members will be required to sign up to the remit and conditions as set out in the DMC Charter.

21 Publication policy

The Publication Policy is detailed in <<document title>> and can be found on the BRAINTRAIN extranet <<file location>>.

22 Milestones

| TASK | START | DURATION | Mo | nths | | | | | | | | | | | | | | | | | | | | |
|--------------|-------|----------|----|------|---|---|---|---|---|---|---|----|----|----|----|----|----|----|----|----|----|----|----|----|
| | | | 1 | 2 | 3 | 4 | 5 | 6 | 7 | 8 | 9 | 10 | 11 | 12 | 13 | 14 | 15 | 16 | 17 | 18 | 19 | 20 | 21 | 22 |
| Recruiting | 1 | 5 | | | | | | | | | | | | | | | | | | | | | | |
| Intervention | 2 | 15 | | | | | | | | | | | | | | | | | | | | | | |
| Follow-up | 8 | 15 | | | | | | | | | | | | | | | | | | | | | | |

23 References

- American Psychiatric Association. (2013). *Diagnostic and statistical manual of mental disorders* (5th ed.). Arlington, VA: American Psychiatric Association.
- Bakeman, R., & Adamson, L. B. (1984). Coordinating attention to people and objects in mother-infant and peer-infant interaction. *Child Development*, *55*(4), 1278–89.
- Baron-Cohen, S. (1989). Perceptual role taking and protodeclarative pointing in autism. *British Journal of Developmental Psychology*.
 Prevalence of autism-spectrum conditions: UK school-based population study. *The British Journal of Psychiatry : The Journal of Mental Science*, *194*(6), 500–9.
 doi:10.1192/bjp.bp.108.059345
- Bellini, S., & Akullian, J. (2007). A Meta-Analysis of Video Modeling and Video Self-Modeling Interventions for Children and Adolescents with Autism Spectrum Disorders. *Exceptional Children*, 73(3), 264–287. doi:10.1177/001440290707300301

1. INTRODUCTION

This statistical analysis plan provides guidelines for the final presentation and analysis for the BCIAUT trial. This plan, along with all other documents relating to the analysis of this trial, will be stored in the Statistical Analysis Master File electronically and/or in hard signed copy formats.

2. BACKGROUND

2.1 RATIONALE AND RESEARCH QUESTION

Autism spectrum disorder (ASD) is a severe, early-onset and life-long neurodevelopmental disorder with a high worldwide prevalence and a distribution of four males (M) to one female (F) (Baron-Cohen et al., 2009; Fombonne, 2003; Oliveira et al., 2007). ASD is characterized by deficits in social interaction and communication as well as by a repetitive pattern of behaviour and interests (American Psychiatric Association, 2013).

Clinical research studies proved that ASD children show a deficit in interpreting others intentions from gaze-direction (Baron-Cohen et al., 1997; Baron-Cohen, 1989). ASD subjects also demonstrated a lack of attentional modulation in a fMRI study especially evident for social stimuli (Bird, Catmur, Silani, Frith, & Frith, 2006).

Individuals with ASD often have relatively strong visual processing skills and a preference towards electronic media, thus it is likely that the dissemination of intervention via computer technology would be particularly appropriate and motivating for these individuals (Shane & Albert, 2008).

The intervention comprises seven BCI sessions spread over four months. In each session, the subject is asked to identify objects of interest based on the gaze direction of an avatar. The subject response is interpreted from the EEG signal (using the P300 component, as established in our previous work).

The purpose of the study is to investigate whether a brain computer interface (BCI) can be used to train social cognition skills (in particular interpretation of gaze direction pointing to objects of interest) in ASD patients and whether this improves clinical symptoms (improvements in identification of social cues and improvement of overall social behaviour).

2.2 OBJECTIVES

The main hypothesis is that training of initiation and response to joint attention cues using gaming/BCI interfaces can be used to improve joint attention social cognition skills in ASD participants.

The primary goal is to ensure increased rate of responses to joint attention cues and improvement of social attention skills.

The secondary objectives are improvements in general aspects of social cognition (as measured by neuropsychological tests) derived from a generalization of the skills learned.

3. STUDY MATERIALS

3.1 TRIAL DESIGN

A Prospective, Single Arm, Longitudinal Cohort Study to assess improvement social attention in ASD (a BCI approach).

The eligible patients for the study will be subject to the same experience during 4 months and will be evaluated before (session 1) and after intervention (session 7 and follow-up).

3.2 RANDOMISATION

Not applicable

3.3 SAMPLE SIZE

To determine de sample size, we used the G*Power tool (Faul, Erdfelder, Lang & Buchner, 2007):

Test family: t-test;

Statistical test: Means (difference between two different means);

Type of power analysis: A priori; Fixed input parameters: Tail(s): Two;

α err prob: 0.05;

Output: Estimated sample size

		Effe	ect Siz	e dz (ES)
		0.8	0.9	1.0	1.1
	0.7	12	10	9	8
Power	0.8	15	12	10	9
	0.9	19	16	13	11

with
$$ES = Cohen's \ dz = \frac{M_{diff}}{\sqrt{\frac{\sum (x_{diff} - M_{diff})^2}{N-1}}}$$
. Based in other effects described in the literature, the effect

size considered is 0.8 (the means difference is 0.8 standard deviations). In these conditions, for power of 0.8 the estimated sample size is 15.

Without the normality assumption of the distribution of the means differences, we would also need 15 subjects, considering a non-parametric test.

Assuming a 20% dropout rate (based on literature) the sample size will be 18.

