4.2 Rationale for current study

The main hypothesis is that training of initiation and response to joint attention cues using gaming/BCI interfaces can be used to improve joint attention social cognition skills in ASD participants.

The BCI setup will be used to train initiation and repeated responses to a joint attention object. An independent game platform will be used to test whether enhanced rates of joint attention (initiation and responses) were achieved.

This study aims to demonstrate that improvements in identification of social cues (and improvement of overall social behaviour) in subjects with ASD can be achieved using social games together with a BCI setup. The primary goal is to ensure increased rate of responses to joint attention cues.

To evaluate the improvements, we will use a new task/realistic game that will challenge the detection of initiation of joint attention cues (from avatars – gaze or pointing). The number of correct responses (to particular objects and not to non-object parts of the scene, will be recorded). We will also record incorrect responses to non-pointing body gestures. Participants will be challenged with about 20 events per minute (one every three seconds), of variable degree of difficulty. Given that the experiment lasts 10 minutes, and some events are control measures, we will have a total of 150 test events and 50 control events. We expect that ASD subjects will be able to correctly report a mean of 75 of the target events, based on tailored task difficulty.

Considering the longitudinal design proposed, with alpha 0.05, power of 80%, and standardized effect of 0.8 (improvement of 8 points for an estimated SD of 10 points) we would need 15 subjects. We will consider three additional subjects to account for drop-offs. The sample size calculations were performed based on a matched 2 sided paired t-test. To determine these values we used the G*Power tool (Faul, Erdfelder, Lang, & Buchner, 2007). The sample size calculations were performed under the assumption that the distribution of the mean differences is normal. Without the normality assumption, we would also need 15 subjects, considering a non-parametric Wilcoxon test.

The structure proposed for this study is the following: (1) initial eligibility screening, (2) preintervention, (3) intervention process, (4) post-intervention, and (5) follow-up.

5 Study objective(s)

5.1 **Primary objective(s)**

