13.2 Sample size

Considering the longitudinal design proposed, with alpha 0.05, power of 80%, and standardized effect of 0.8 (improvement of 8 points for and estimated SD of 10 points) we would need 15 subjects (plus 3 in case of drop outs). We will add three additional subjects to account for drop-offs. The sample size calculations were performed based on a matched 2 sided paired t-test. To determine these values we used the G*Power tool (Faul et al., 2007). The sample size calculations were performed under the assumption that the distribution of the mean differences is normal. Similarly, without the normality assumption, we would also need 15 subjects, considering a non-parametric Wilcoxon test.

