6.3.3 ASSUMPTION CHECKING

The Shapiro Wilks test will be performed to evaluate the normality.

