6.3.4 ALTERNATIVE METHODS IF DISTRIBUTIONAL ASSUMPTIONS NOT MET

Without the normality assumption, we will consider a non-parametric tests: Friedman test and Wilcoxon or Sign test. Since the primary outcome is a count variable it may be more suited to methods that utilize the Poisson distribution. If the primary outcome conforms to a Poisson distribution rather than a normal distribution then Poisson regression will be considered. Effect estimates and 95% confidence intervals will be tabulated.

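### SAP 3.3: 18 enrolled keeps 15 evaluable only up to 16.7% dropout, not the stated 20%, and the non-parametric figure of 15 belongs to the Wilcoxon test, not to the Sign test that SAP 6.3.4 also allows

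*SAP*

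**What the plan says.** SAP 3.3 sizes the study for a two-sided 0.05 test with a standardised paired difference (dz) of 0.8: "for power of 0.8 the estimated sample size is 15". For the case where normality fails it adds that "we would also need 15 subjects, considering a non-parametric test", without naming the test. It then allows for losses: "Assuming a 20% dropout rate (based on literature) the sample size will be 18".

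The protocol is narrower on both counts. Section 4.2 gives a number and no dropout rate: "We will consider three additional subjects to account for drop-offs". Section 13.2 does the same, and ties the second figure of 15 to a named test: "without the normality assumption, we would also need 15 subjects, considering a non-parametric Wilcoxon test". Section 15.1 names that same test as the only fallback: "without the normality assumption, we will consider a non-parametric Wilcoxon test".

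In the SAP's analysis section the only stated distributional check is in 6.3.3: "The Shapiro Wilks test will be performed to evaluate the normality". If normality is not met, 6.3.4 says "we will consider a non-parametric tests: Friedman test and Wilcoxon or Sign test". It gives no rule for choosing between the last two.

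**The concern.** The dropout sentence links three figures (15 needed, 20% lost, 18 enrolled) that do not fit together. A reader would take 18 to mean that 15 evaluable participants remain after a 20% loss.

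The non-parametric sentence has moved from a specific claim in the protocol to a general one in the SAP, while the SAP's list of permitted tests has grown to include one with different power. A reader could assume 80% power for whichever test is eventually used. The normality check decides whether the normal-theory analysis is kept. It does not decide which pairwise test replaces it, so that choice stays open until the data are seen.

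**Working it through.** **Inputs.** Two-sided alpha 0.05, dz 0.8, power 0.80, 20% dropout and 18 enrolled (SAP 3.3). Paired t-test, improvement of 8 points with SD 10, and three extra participants (protocol 13.2). All power figures are for complete pre-post pairs, the comparison used for sizing.

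**1. The plan's own 15.** Paired-t power is P(|T| > t(0.975, n−1)), with T noncentral t on n−1 df and noncentrality 0.8√n.
- n = 15: noncentrality 3.098, critical value 2.145, power 82.1%.
- n = 14: noncentrality 2.993, critical value 2.160, power 79.0%.

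So 15 is the smallest n reaching 80%. All 12 cells of the SAP 3.3 table reproduce.

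**2. Dropout allowance.**
- Needed for 15 evaluable at 20% loss: 15/(1 − 0.20) = 18.75, so 19.
- Eighteen equals 15 × 1.20, although the SAP does not show its formula.
- Largest loss that leaves 15 of 18: 3/18 = 16.7%.
- Expected completers at 20% loss: 18 × 0.80 = 14.4.

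If each participant drops out independently with probability 0.2:

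| Enrolled | P(at least 15 remain) | Average paired-t power | Average Wilcoxon power (normal differences) |
|---|---|---|---|
| 18 | 50% | 79.7% | 77.1% |
| 19 | 67% | 82.1% | 79.6% |

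With 18 enrolled, average paired-t power falls below 80% once dropout exceeds about 19.5%.

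**3. Wilcoxon signed-rank at n = 15.** Under normal differences the asymptotic-relative-efficiency method (3/π) gives 80.1%, and simulation with exact critical values gives 80.0%. At n = 14 simulation gives about 77%. The protocol's 15 therefore reproduces, with the caveat that it rests on a normal shape; the least favourable efficiency (0.864) would give 17.

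**4. Sign test at n = 15.** It rejects at 12 or more, or 3 or fewer, positive differences. The actual alpha is 2 × (455 + 105 + 15 + 1)/32,768 = 0.035. Power of 80% needs P(difference > 0) of at least about 0.843. Under normal differences P(difference > 0) = Φ(0.8) = 0.788 and power is 60.3%; the smallest n reaching 80% is then 23.

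The documents give no shape for the differences, so a range is shown, all at dz = 0.8 and n = 15:

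| Assumed shape | P(difference > 0) | Sign | Wilcoxon |
|---|---|---|---|
| Uniform | 0.731 | 39% | 74% |
| Normal | 0.788 | 60% | 80% |
| Right-skewed exponential | 0.819 | 72% | 97% |
| t, 5 df | 0.825 | 74% | 85% |
| Left-skewed exponential | 0.835 | 77% | 80% |
| Laplace | 0.839 | 79% | 85% |
| t, 3 df | 0.870 | 88% | 92% |

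These powers are not conditioned on the normality check (see the objection).

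**5. Free choice between the two.** Under the null at n = 15 with symmetric continuous differences, Wilcoxon alone rejects 4.8%, Sign alone 3.5%, and at least one of them 6.0%.

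**The case against.** **The dropout error is one participant.** This is correct. The study is a single-arm trial that SAP 6.1 calls a feasibility trial, three is 20% of 15, and power at the expected number of completers stays near 80%. A reader might infer that the trial is materially underpowered or must enrol 19. The figures do not support that. Nor is the protocol wrong: it adds three participants and states no rate. What stands is that the SAP sentence misstates what 18 delivers.

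**All participants are analysed (SAP 4.3) and missing values are mean-imputed (SAP 6.4), so n stays at 18.** Imputed means do not restore lost information, and SAP 3.3 itself treats dropout as a loss to be offset.

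**The Sign test is used only after normality fails.** This is a fair limit on the Sign figures. A reader might infer that the planned fallback has 60% power. That is an unconditional figure for a shape that fails Shapiro-Wilk in only about 5% of samples of 15. Among samples that do fail, Sign power is about 70% (normal), 80% (t with 5 df and left-skewed exponential), 86% (Laplace) and 90% (t with 3 df). It stays lower for the right-skewed exponential (about 67%) and the uniform (in the low 20s). So 15 is not supported for Sign in general, but the shortfall depends on a shape that the documents do not state.

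**The 6.0% shows inflated error.** It is only indicative. It ignores the normality check and any preceding Friedman test, and it assumes continuous symmetric differences. The primary outcome is a count, with possible ties and zero differences.

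**The Sign test protects against asymmetry.** It does so for a median hypothesis: with exponential differences of median zero, Wilcoxon rejects 8.1% and Sign 3.5%. Protocol 15.1, however, states its null for the mean difference. With exponential differences of mean zero, Sign rejects about 14%, Wilcoxon about 11% and the t-test about 8.5%. Switching to Sign when sample skewness is large might look like a remedy, but at n = 15 with median-zero exponential differences such a rule rejects about 5% to 8% for cut-offs from 0.5 to 1.5, against 3.5% for Sign alone.

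**Conclusion.** Both points hold and both are minor.

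The dropout sentence in SAP 3.3 is wrong as written. Relative to the 80% target, the shortfall at 20% dropout is up to about 1 point for the paired t-test (79.0% at 14 completers, 79.7% averaged) and about 3 points for Wilcoxon under normal differences (77.1% averaged).

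The SAP's non-parametric wording is wider than the calculation behind it. Fifteen is supported for the Wilcoxon signed-rank test under normal differences. It is not supported in general for the Sign test, which the protocol names neither for sizing nor as a fallback. SAP 3.3 does not itself say that 15 was computed for Sign; the gap comes from reading its general wording together with SAP 6.3.4.

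These conclusions rest on dz = 0.8, complete pre-post pairs, independent dropout for the averaged figures, and the shapes listed. They say nothing about the power of the three-time-point ANOVA or the Friedman test.

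**What to change.** **SAP 3.3, dropout sentence.** Replace it with: *Enrolling 18 gives 15 evaluable participants at up to 16.7% dropout. At 20% dropout about 14 are expected, with power of about 79% to 80% (paired t-test) or about 77% (Wilcoxon signed-rank, normal differences), for complete pre-post pairs at dz = 0.8. These figures do not apply to the three-time-point ANOVA or the Friedman test.*

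**SAP 3.3, preceding sentence.** Name the Wilcoxon signed-rank test in place of the general non-parametric wording, as protocol 13.2 does.

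**SAP 6.3.4.** Name Wilcoxon signed-rank as the pairwise fallback, consistent with protocol 15.1. If a Sign test is reported, label it as supplementary, say that it tests the median difference, and state that 15 was not computed for it.

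**Cost.** Wording in two SAP sections and no extra participants. The stated power becomes slightly less favourable, and the Sign test is no longer an alternative main fallback.

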3.4 FRAMEWORK

The trial protocol states the main objective is that training of initiation and response to joint attention cues using gaming/BCI interfaces can be used to improve joint attention social cognition skills in ASD participants. Therefore, the main outcomes are testing for superiority rather.

Short title:

BRAINTRAIN SAP Template

[figure not shown]
3.5 INTERIM ANALYSES

Not applicable.

- 3.5.1 PLANNED SAMPLE SIZE ADJUSTMENT
- 3.5.2 STOPPING RULES
- 3.6 TIMING OF FINAL ANALYSIS

The intervention comprises seven BCI sessions spread over four months. In each session, the subject is asked to identify objects of interest based on the gaze direction of an avatar. Each subject will also undergo neuropsychological evolutions and "Joint-attention task" before the first session, after the last session (short-term) and in follow-up (long-term).

